| statistical method | Baseline data were analyzed by Chi-square test. Measurement data are expressed as mean SD. Univariate analysis of variance was used to compare the difference between groups at the same time point, the difference at different time points in the group, and the difference before and after between the two groups. $P < 0.05$ was considered statistically significant, and multiple comparisons were performed by Dunnett-t test.   |
| Expected progress  | Clinical cases will be collected from 2023.1.1 to 2024.12.30, and insufficient cases due to shedding will be added from 2025.1.1 to 2025.12.30.  |

List of abbreviations and term definitions

| abbreviation | definition                          |
|---------------------|--|
| CRS-R               | Coma Recovery Scale-Revised                |
| GCS                 | glasgow coma scale                         |
| NIHSS               | National Institutes of Health Stroke Scale |
| FOUR                | Full Outline of Unresponsiveness Scale     |

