## **3.study endpoint**

3.1 Primary endpoint: GCS score.

3.2 Secondary endpoints: CRS-R Scale (Coma Recovery Scale-Revised), EEG(electroencephalograph), BAEP (Brainstem Auditory Evoked Potential), and EFG (Encephalofluctuography).

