### **(2) Evaluation:**

Consciousness levels were assessed before intervention, at 1, 2, 3, and 4 weeks of treatment, and 4 weeks after discharge: GCS score, NIHSS score, CRS-R Scale (Modified Coma Recovery Scale), and FOUR scale score . Electroencephalogram, brainstem auditory evoked potentials and encephalofluctuograph were examined before intervention and at 4 weeks of treatment.

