### **13.3 Statistical method**

The analysis included case distribution, demographic data, baseline analysis and therapeutic effect analysis. Baseline data included sex, age, stroke type, stroke duration, underlying medical history (diabetes, hypertension, heart disease, chronic obstructive pulmonary disease), and history of smoking and alcohol use. Baseline data were tested by chi-square test. The end point data was the score of the State of Consciousness scale, and the measurement data was expressed as mean SD. Univariate analysis of variance was used to compare the difference between groups at the same time point, the difference at different time points in the group, and the difference before and after between the two groups.  $P < 0.05$  was considered statistically significant, and multiple comparisons were performed by Dunnett-t test.

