### **13.4 Statistical software and general requirements:**

- 1)All statistical analysis was performed using SPSS25.0 statistical software.
- 2)Measurement data were described using mean, standard deviation, median, maximum and minimum values.
- 3)Counting data are described by frequency and percentage.
- 4)All data in the experiment were tested for normality.
- 5)Baseline data were analyzed using Chi-square test. Measurement data are expressed as mean SD. Univariate analysis of variance was used to compare the difference between groups at the same time point, the difference at different time points in the group, and the difference before and after between the two groups.  $P < 0.05$  was considered statistically significant, and multiple comparisons were

performed by Dunnett-t test.

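### Within-group change over six visits is tested with an independent-samples ANOVA and Dunnett-t that ignore the pairing, so these tests are conservative and can lose much of their power

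*Combined protocol and SAP*

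**What the plan says.** Section 13.3 names a single method, univariate analysis of variance, for three kinds of comparison. The first sets the two arms against each other at a given visit. The other two are "the difference at different time points in the group, and the difference before and after between the two groups". It goes on to say that P<0.05 "was considered statistically significant, and multiple comparisons were performed by Dunnett-t test". The statistical-method row of the Summary of research scheme repeats this ("multiple comparisons were performed by Dunnett-t test"), as does item 5 of section 13.4 ("performed by Dunnett-t test").

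The data are repeated scores. Section 7.2 (2) states: "Consciousness levels were assessed before intervention, at 1, 2, 3, and 4 weeks of treatment, and 4 weeks after discharge". That makes six assessments per patient, and the test flow chart shows the same six for GCS, CRS-R, NIHSS and FOUR. Section 13.3 identifies what is analysed: "The end point data was the score of the State of Consciousness scale". Section 3.1 gives the "Primary endpoint: GCS score" without naming a visit or a test.

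No section mentions a paired test, repeated-measures ANOVA, a mixed model, a patient effect or a within-patient covariance.

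**The concern.** Analysis of variance without a patient term, followed by Dunnett-t, compares independent samples. Used across visits within one arm, it treats the six scores of one patient as if they came from six different people. Its error term is then the spread between patients, whereas the precision of a within-group change depends on how much each patient's change varies.

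Dunnett-t compares several groups with one control. With two arms it has no such role between groups, so its natural use here is each later visit against baseline, which is where the pairing matters.

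At stake is whether the within-group results can be read. The plan gives them the same 0.05 threshold as the between-group tests and does not mark them as descriptive. A real change within an arm may be reported as not significant because the test discarded the pairing.

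**Working it through.** **Inputs.** Six assessments per patient (section 7.2 and the flow chart); significance level 0.05 (section 13.3); 87 per group (section 13.1). The documents give neither an SD nor a within-patient correlation. Effects are therefore in SD units, and the correlation is assumed and ranged.

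**The plan's own figure.** It states none for the within-group tests. Its sample size does reproduce: P = (0.794 + 0.548)/2 = 0.671, and 2 × (1.96 + 1.28)² × 0.671 × 0.329 / 0.246² = 76.6, stated as about 76. Then 76 × 1.15 = 87.4, stated as 87. (Section 4 gives a total of 72 instead of 174. That is a separate matter, and the ratio in step 1 does not depend on n.)

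**Step 1: standard error.** Take two visits with common SD s and correlation r between them.
- Independent-samples SE of the difference: sqrt(2s²/n).
- Correct SE for the same patients: sqrt(2s²(1 − r)/n).
- Ratio: 1/sqrt(1 − r).

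| r | 0 | 0.3 | 0.5 | 0.7 | 0.9 |
|---|---|---|---|---|---|
| SE too large by | 1.00 | 1.20 | 1.41 | 1.83 | 3.16 |

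**Step 2: direction.** An SE that is too large makes P too large. In 4,000 simulated trials with 76 patients and no true change, the nominal 5% F test rejected in 4.8% at r = 0, 0.6% at r = 0.3 and 0.05% at r = 0.5, with all visits equally correlated. With correlation decaying by visit (AR(1)), it rejected in 3.3% at lag-1 correlation 0.3 and 1.0% at 0.7. When the SD was allowed to grow from 1 to 2.3 across visits, the chance of any Dunnett rejection stayed below 5%: 2.8% at r = 0, 1.2% at 0.3 and 0.25% at 0.5.

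**Step 3: power for a true 0.3 SD gain at week 4, n = 87.** The planned SE is sqrt(2/87) = 0.1516 SD, so the expected statistic is 0.3/0.1516 = 1.979. The Dunnett critical value (five comparisons, 516 df) is 2.516. The statistic's true SD is sqrt(1 − r), not 1.
- Planned test: P(Z > (2.516 − 1.979)/sqrt(1 − r)).
- Paired test with Bonferroni over five comparisons (t critical value 2.634 on 86 df): approximately P(Z > 2.634 − 1.979/sqrt(1 − r)).

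At r = 0.7, sqrt(0.3) = 0.548. The planned test gives P(Z > 0.98) = 16%, and the paired test gives P(Z > −0.98) = 84%. Simulation gives 17% and 84%. Under AR(1), week 4 is four visits from baseline, so lag-1 0.7 gives r = 0.7⁴ = 0.24 and lag-1 0.5 gives r = 0.5⁴ = 0.06.

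| Assumed correlation | Planned Dunnett-t (simulated) | Paired, Bonferroni (simulated) |
|---|---|---|
| Equal, r = 0.7 | 17% | 84% |
| Equal, r = 0.5 | 22% | 56% |
| AR(1), lag-1 0.9 | 19% | 76% |
| AR(1), lag-1 0.7 | 27% | 36% |
| AR(1), lag-1 0.5 | 29% | 29% |

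**Step 4: reach.** A between-group test at one visit uses one score per patient. A between-group test of before-after differences uses one change per patient. Neither treats repeated scores as independent. The sample size compares two effective rates and does not use the within-group tests.

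**The case against.** The strongest reply is that little depends on this. The trial is a randomised sham-controlled comparison. Section 13.3 supplies two between-group analyses that do not have the defect, and the error is conservative where it does occur. The loss is also uncertain: under serial decay it may be small or absent. Finally, the text says univariate, not one-way, so the authors may have had a suitable model in mind. Most of this stands, and it limits the severity. The last point does not rescue the text: nothing in it names a patient effect, and Dunnett-t points to independent samples.

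A reader might infer three stronger things that the documents do not support.

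- *That significance in one arm only would be a product of the wrong test.* With the same true gain in both arms, n = 87 and equal correlation 0.7, one-arm-only significance occurs in 48% of trials under Dunnett-t and about 2% to 4% under the paired test for a 0.4 SD gain. For 0.3 SD the figures are about 29% and 27%, and for 0.2 SD they reverse, to about 4% and 47%. The problem comes from comparing two within-group P values, whichever test produces them.
- *That drop-out would make a group appear to improve.* A rise of 0.15 SD in the mean would follow from the planned 15% shedding if leavers scored 1 SD below stayers (0.15 × 1). The documents give no such gap and do not say how missing visits are handled, and the per-protocol set in 13.2 is limited to patients who completed protocol treatment.
- *That the reported error bars would be wrong.* The plan describes scores by mean and SD at each visit, and an SD at one visit does not depend on pairing. Only the test is affected.

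**Conclusion.** The within-group analysis is wrong as written, because it applies an independent-samples method to six scores from the same patients. The consequence is inflated standard errors and lost power, not false positives. The inflation is 1.20 to 3.16 for a between-visit correlation of 0.3 to 0.9. The power loss for a 0.3 SD week-4 gain ranges from none (AR(1), lag-1 0.5) to 67 percentage points (equal correlation 0.7: 84 − 17).

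These sizes rest on assumed positive correlations, equal variances across visits, complete data on 87 patients per group, and Dunnett-t being used against baseline. The direction needs only that a patient's scores correlate positively, which is to be expected. The estimate of the treatment effect, its between-group tests and the sample size do not have this defect. The text should be corrected, but the main comparison does not fail because of it.

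**What to change.** In the statistical-method row of the Summary, in 13.3 and in 13.4 item 5, replace the within-group ANOVA and Dunnett-t with a method that takes the patient as the repeated unit. Either of these would serve:

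- a mixed model for each scale with arm, visit and arm-by-visit effects and a stated within-patient covariance structure; or
- paired contrasts of each later visit against baseline, with a stated multiplicity adjustment.

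Report within-group changes with 95% confidence intervals. State that they are descriptive and that the efficacy conclusion rests on the between-group comparison. This point alone does not require any change to the between-group analyses.

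The cost is SAP wording and slightly more analysis work in SPSS, which can fit such a model. No new data, visits or patients are needed. The change should be made before the database is locked.

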### **13.4 Statistical software and general requirements:**

- 1)All statistical analysis was performed using SPSS25.0 statistical software.
- 2)Measurement data were described using mean, standard deviation, median, maximum and minimum values.
- 3)Counting data are described by frequency and percentage.
- 4)All data in the experiment were tested for normality.
- 5)Baseline data were analyzed using Chi-square test. Measurement data are expressed as mean SD. Univariate analysis of variance was used to compare the difference between groups at the same time point, the difference at different time points in the group, and the difference before and after between the two groups.  $P < 0.05$  was considered statistically significant, and multiple comparisons were

performed by Dunnett-t test.

## **14. testing management**

### **14.1 Comply with GCP requirements**

Governing body and implementation of the GCP:

- 1) Drug registration applicants and investigators should adopt standard operating procedures to implement quality control and quality assurance systems for clinical trials;
- 2) The original data must meet the GCP requirements of our country;
- 3) Laboratory test results must be accurate and reliable;
- 4) The observations and findings used should be verified to ensure the reliability of the data;
- 5) Establish a complete test organization and clarify the responsibilities of personnel at all levels;
- 6) The main researcher shall be responsible for the overall quality control and carry out the responsibilities of personnel at all levels;
- 7) The main investigator shall be responsible for the design of the experimental protocol and informed consent, and the main investigator shall write the experimental summary report after the end of the experiment;
- 8) The designated researcher shall be responsible for developing the implementation rules and SOP for use in the test;
- 9) The study plan for all participants shall be organized by the test group before the experiment, and all participants shall undergo GCP training;
- 10) The doctors, nurses and therapists participating in the experiment shall strictly abide by the protocol and follow the procedure, and shall not change it at will;
- 11) Designated statisticians are responsible for the overall statistical processing of the data.

### **14.2 Protect the subject's privacy**

All the data of the subjects during the experiment will be recorded into the computer for confidential storage and analysis. If necessary, the records may be reviewed by relevant institutions to confirm the truth, accuracy and completeness of

the data. The data obtained from the experiment may also be published in academic journals, but the names of the subjects will not be published and the privacy of the subjects will be kept confidential.

Extra precautions are taken to ensure confidentiality of documents and to prevent identification of subjects through genetic data. However, in exceptional circumstances, someone may see a subject's genetic data and personal identification number. For example, in the event of a medical emergency, the sponsor, its representative physician or investigator is aware of the subject identification number and has access to the subject's genetic data. In addition, the relevant regulatory authorities requested access to the relevant documents.

### **14.3 Problems arising in the test and their treatment measures**

- 1) Revision of the protocol: After the protocol is approved by the Ethics Committee, if the protocol is to be revised, a "Protocol Revision Statement" shall be formulated and signed by the principal investigator. The scheme can only be revised with the consent of the researcher and the applicant for drug registration through consultation;
- 2) The revised plan shall be submitted to the Ethics Committee for review and approval before implementation;
- 3) Any adverse event (AE) or severe adverse event (SAE) that occurs during the test will be reported and handled in accordance with the requirements of the protocol and SOP.

### **14.3 Quality control and quality assurance**

#### **14.3.1 quality assurance:**

The sponsor and the cooperating units entrusted by the sponsor to be responsible for all or part of the responsibilities and tasks related to this study (including CRO, SMO, statistical unit, clinical center, etc.) shall establish their own quality assurance systems, perform their respective duties, strictly follow the clinical trial protocol, and adopt the corresponding standard operating procedures. To ensure the implementation of clinical trial quality control and quality assurance system.

#### **14.3.2 Quality assurance of clinical trial process**

Before starting clinical trials, researchers should receive training on the trial protocol, so that researchers have a full understanding of the clinical trial protocol and the specific connotation of each indicator. Quality control personnel should check the basic conditions of clinical trials to ensure that clinical trial conditions can meet the requirements of the program. In the course of the trial, the investigator shall carefully perform the clinical operation and other work according to the institutional SOP and the requirements of the trial protocol, and record it in a true, timely, complete and standardized manner. Quality control personnel conduct quality verification of the test process and corresponding original records. After the end of the test, the research unit sorted out the corresponding project files, which were checked by the quality control personnel and archived. The quality assurance department of the clinical research unit shall check the feasibility of the trials conducted. When non-conforming items are found, timely notify the researcher and the head of the unit to correct, and track the correction.

#### **14.4 The expected schedule and completion date of the clinical trial**

- 1)2023.1.1~2024.12.30: Clinical cases were collected
- 2)2025.1.1~2025.12.30: Cases of deficiency due to supplementary Shedding

#### **14.5 Sponsor's duties**

The sponsor is responsible for initiating, applying for and organizing this clinical trial, and providing trial funds. The sponsor shall submit the application for clinical trial to the State Food and Drug Administration in accordance with the provisions of China's GCP, drug registration Administration and other regulatory documents, and may also entrust a contract research organization (CRO) to perform certain work and tasks in the clinical trial.

The sponsor selects the institution and investigator of the clinical trial and recognizes its qualifications and conditions to ensure the completion of the trial.

In providing experimental drugs to researchers, sponsors shall establish a management system and record system for experimental drugs.

##### **14.5.1 Researcher responsibility**

This clinical study will be conducted in accordance with the moral, ethical and

scientific principles as well as protocol design and regulations stipulated by the Declaration of Helsinki and the Chinese GCP.

The investigator is responsible for making medical decisions related to the clinical trial to ensure that the subject receives timely treatment if AE occurs during the trial. Researchers should be aware of the procedures and requirements for reporting SAE, and record and report these events as required.

The researcher shall accurately, completely, timely and legally load the data into the eCRF, and accept the supervision or audit of the sponsor or CRO company and the inspection and inspection of the drug regulatory department to ensure the quality of the clinical trial.

#### **14.5.2 Sponsor research methods for data publication**

The sponsor has exclusive rights to this research data. Individual contributions should not be published until the final report of the multi-centre study has been completed, except with the written consent of the sponsor. The Sponsor has the final say in respect of the manuscript and publication.

### **15. Ethics related to trials**

#### **15.1 Ethics committee**

The investigator shall submit the Investigator Handbook, protocol, informed consent, CRF and test drug inspection Report (as submitted), and any other information to the subject to the Ethics Committee for approval prior to the commencement of the study. Any amendments to the protocol must be approved by the Ethics Committee.

#### **15.2 Informed consent**

In informed consent, a qualified investigator must explain in detail to each subject the nature, purpose, procedure, expected time, potential risks and benefits, and any discomfort that may arise. Each subject must be aware that participation in the trial is voluntary and that he/she may withdraw from the trial and withdraw informed consent at any time without affecting his/her subsequent treatment or relationship with the treating physician.

Informed consent should be given in a standard writing format and in

non-professional language as far as possible. Each informed consent form must include all of the above and include a voluntary declaration. Informed consent must be submitted to the Ethics Committee for approval.

After the basics of the trial have been explained and the investigator is satisfied that each subject understands the purpose of the trial, each subject should be asked to sign and date the informed consent form. Subjects should read and consider their statements before signing and dating them, and should obtain an informed consent form to keep after signing. Subjects are not allowed to enter the study without informed consent.

### **15.3 other**

When the subject is unable to participate independently in informed consent, a reliable and fair witness/legal representative must be present throughout the informed consent process. The selection of fair witnesses/legal representatives shall not violate the subject's right to confidentiality. After the subject has given verbal consent, the fair witness/legal representative should sign and date the informed consent to certify that the information is accurate.

